#### **5.4. Conditions for storage of study treatment**

TRISENOX® and ARSCIMED® will be stored in a secure location at 25°C (77°F); excursions will be permitted to 15-30°C (59-86°F), but TRISENOX® must not be frozen and ARSCIMED® must not be refrigerated or frozen.

After dilution of TRISENOX® in intravenous solutions, ATO is chemically and physically stable for 24 hours at 15-30°C and 48 hours at refrigerated (2-8°C) temperatures. From a microbiological point of view, the product must be used immediately. If not used immediately, in-use storage times and conditions prior to use are the responsibility of the user and would normally not be longer than 24 hours at 2-8°C, unless dilution has taken place in controlled and validated aseptic conditions.

After dilution of ARSCIMED® in intravenous solutions, ATO is chemically and physically stable for 4 hours at 15-25°C. The product must not be stored at refrigerated (2-8°C) temperatures after dilution since its stability under these conditions has not been studied yet. From a microbiological point of view, the product must be used

immediately.

## 6. Concomitant treatments

### 6.1. Ciclosporine A

- Ciclosporine A will be delivered using local standard criteria, (if relevant). However:
  - Ciclosporine level should lie within the therapeutic range (i.e. 200-400 ng/mL): to harmonize CsA target levels
  - Ciclosporine-induced renal insufficiency should lead to dose adjustment and even temporary withdrawal of the drug
- Suggested guidelines for initial dose of Ciclosporine A:

Oral administration of ciclosporine should continue for patients who are being treated with ciclosporine at the time of enrolment, or if it is relevant, the administration should commence initially at 6mg/kg daily.
- Monitoring of ciclosporine level:
  - Concentrations of ciclosporine in the plasma may be monitored at the discretion of the investigator. Dose adjustments may be made to maintain ciclosporine concentrations at 200-400 ng/ml. Monitoring may be especially helpful in patients with renal impairment and in patients being treated with medications that may affect the concentration of ciclosporine.
  - Medications that could increase the concentration of ciclosporine include diltiazem, nicardipine, verapamil, metoclopramide, ketoconazole, fluconazole, itraconazole, erythromycin and methylprednisolone.
  - Medications that could decrease the concentration of ciclosporine include rifampycin, phenytoin, phenobarbital and carbamazepine.

➤ Deviations from guidelines for administration of ciclosporine

Deviations from the above guidelines may be made at the discretion of the investigator in consultation with the transplant centre. Toxicity associated with the administration of ciclosporine may require dose adjustments, which should be managed according to individual transplant centre practice.

## 6.2.Prednisone

➤ The initial dose of prednisone is 1.0 mg/kg/day, this dose should be maintained for 2 weeks, after which a tapering schedule should commence up until response assessment at 6 weeks, after which treatment is as follows:

- CR: continue tapering of Prednisone dose (see Table below)
- No CR: maintain Prednisone dose at 1 mg/kg/day on alternate days or 0.5 mg/kg/day every day

Usual prevention of steroid-induced gastro-intestinal (GI) side effect should be given (omeprazole or other drugs, according to local practice).

➤ The investigator will determine the regimen for administration of prednisone after enrolment in the study. The following taper schedule is given as a general guideline:

**Table 1 : Prednisone Taper Schedule**

Week	Dose (mg/kg actual body weight/day)
0	1.0 qod
2	0.75 qod
4	0.65 qod
6	0.50 qod (if CR, continued tapering of corticosteroids dose) 0.50 qod (if No CR, maintain this dose until resolution of all reversible clinical manifestations or adjust the required dose)
8	0.40 qod
10	0.30 qod
12	0.20 qod
14	0.15 qod
20	0.0

- The investigator should examine the patient before each reduction in the dose of prednisone. If there is exacerbation or recurrence of chronic GvHD at any step of the taper, the dose of prednisone should be increased by 2 levels with daily administration for 2-4 weeks, followed by resumption of alternate day administration. Prednisone may be discontinued after 2 weeks of treatment at a dose of 0.15 mg/kg every other day. Qod prednisone dosing is not required, and the use of qod dosing is at the discretion of the investigator. It is suggested, but not required, that patients taper off steroids before tapering of other immunosuppressive medications.
- Toxicity associated with the administration of prednisone should be managed according to individual transplant center practice.

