Investigational product	
Arsenic trioxide 10 mg, concentrate for solution for infusion 1 mg/mL (aqueous sterile, clear, colorless).
 
Arsenic trioxide is administrated either via the marketed product named TRISENOX® or the investigational medicinal product named ARSCIMED®.
 
Patients under TRISENOX® treatment will not switch to ARSCIMED® treatment nor vice versa:
 
 
- Patients already recruited and receiving TRISENOX® will continue receiving only TRISENOX®
 
- All patients recruited after this amendment has been approved will receive ARSCIMED® only and not TRISENOX®.
 
 
Treatment scheme
 
As soon as the diagnosis of chronic GvHD requiring systemic immunosuppressive therapy is confirmed, patients will receive in addition to corticosteroids (prednisone) 1 mg/kg/day, with or without cyclosporine A, a daily infusion of ATO 0.15 mg/kg/day on days 1 to 5 (first week), 3 times per week during the second week (for example, days 8, 10 and 12), 2 times per week during the third week (for example, days 15 and 17) and one time during the fourth week (for example, day 24) (the latter four weeks represent one cycle).
 
ATO should be administered within 10 days of starting prednisone at 1mg/kg/day for cGvHD treatment. Follow-up dates for response assessment and laboratory tests relate to the date of ATO infusion.
 
Patients who are in partial response after the 1st cycle of ATO will be eligible to receive a second cycle of ATO infusions during 4 weeks (similar schedule to first cycle starting around day 60). In another word, a delay of 8 weeks to a maximum of 11 weeks (from the first infusion of ATO) will be observed between the two cycles of ATO therapy.
 
Response definition is as follows:
 
 
- Complete remission (CR) is defined as complete disappearance of any sign of chronic GvHD
 
- Partial remission (PR) is defined as improvement of 1 or more point on a 4 to 7-point scale or an improvement of 2 or more points on a 10 to 12-points scale in at least 1 organ or site without progression in any other organ or site. For patients with Bronchiolitis Obliterans Syndrome (BOS), an absolute improvement in % FEV1 of 10% predicted or more (eg, 50% to 60%) is considered a PR as long as the initial % FEV1 is < 70%. Normalization (<math>\geq 80\%</math>) is considered a CR.
 
- Failure is defined as death, recurrent or progressive malignancy or the initiation of new systemic treatment for chronic GvHD. Increased dosing of existing treatment will not be considered as failure. Early failure is defined as failure within 2 weeks after the end of the first ATO cycle.
 

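### Protocol 6.2 contradicts its own Table 1 on prednisone: read literally, the table's qod rows average half the text's dose at week 0 and at week 6 without CR, and SAP 9.3.6.2 copies both

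*Protocol*

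**What the plan says.** Protocol 6.2 gives prednisone doses twice, first in text and then in Table 1.

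- **Start, text:** "The initial dose of prednisone is 1.0 mg/kg/day, this dose should be maintained for 2 weeks". The Synopsis agrees ("patients will receive in addition to corticosteroids (prednisone) 1 mg/kg/day, with or without cyclosporine A"), and Protocol 5.1 and 7.3.2.1 give the same starting dose.
- **Start, Table 1:** the week-0 row reads 1.0 qod.
- **Week 6 without CR, text:** "No CR: maintain Prednisone dose at 1 mg/kg/day on alternate days or 0.5 mg/kg/day every day".
- **Week 6 without CR, Table 1:** "0.50 qod (if No CR, maintain this dose until resolution of all reversible clinical manifestations or adjust the required dose".
- **Unit of Table 1:** the column is headed "Dose (mg/kg actual body weight/day", yet every non-zero row is marked qod.

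Three sentences qualify the table. It is introduced with "The following taper schedule is given as a general guideline". The investigator sets the regimen after enrolment. Below the table stands "Qod prednisone dosing is not required, and the use of qod dosing is at the discretion of the investigator".

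SAP 9.3.6.2 repeats both the text and the table. SAP 11.4.2.3 derives the daily prednisone dose as dose times frequency divided by weight, sorts it into bands at W6, W14, M6, M9 and M12, and classes the change of band from baseline as decreased, unchanged or increased.

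**The concern.** Text and table sit in the same section and should describe the same regimen. If qod means what it says, a site working from Table 1 gives half the average daily dose of a site working from the text, both at the start and when holding the dose without CR. Both sites could say that they followed section 6.2.

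This matters for interpretation. There is one arm, tested against a fixed 60% response rate, and prednisone is an active treatment given alongside ATO. A difference in steroid exposure cannot be separated from an ATO effect on the M6 response. Steroid dose is also a secondary endpoint, so the same ambiguity enters the dose bands that will be reported.

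**Working it through.** **Convention.** Average daily dose = amount per administration ÷ dosing interval in days (1 for daily, 2 for every other day).

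**Check against the plan's own equivalence.** The text offers two options without CR at week 6:
- 1 mg/kg on alternate days: 1.0 ÷ 2 = 0.50 mg/kg/day
- 0.5 mg/kg every day: 0.5 ÷ 1 = 0.50 mg/kg/day

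The two agree, so the convention is the one the protocol uses. The literal reading of qod in Table 1 is supported by the sentence on its last dose level: "Prednisone may be discontinued after 2 weeks of treatment at a dose of 0.15 mg/kg every other day".

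**Text against Table 1, qod read literally**

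| Point | Text, mean mg/kg/day | Table 1, mean mg/kg/day | Ratio |
|---|---|---|---|
| Week 0 | 1.0 ÷ 1 = 1.0 | 1.0 ÷ 2 = 0.50 | 2.0 |
| Week 6, no CR | 0.50 | 0.50 ÷ 2 = 0.25 | 2.0 |

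If the qod label is ignored, the table shows 1.0 and 0.50 and matches the text at both points. The conflict therefore lies in the qod labels set against the column header and the text. Nor can the text's no-CR line simply be joined to the qod table: the week-4 row averages 0.65 ÷ 2 = 0.325 mg/kg/day, so holding at 0.50 from week 6 would be a rise.

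**Cumulative size**
- Weeks 0-2: 14 days × 1.0 = 14 mg/kg, against 14 × 0.5 = 7 mg/kg.
- No CR, assuming a constant, unadjusted dose for 20 weeks (week 6 to about week 26): 140 × 0.50 = 70 mg/kg, against 140 × 0.25 = 35 mg/kg. Table 1 allows the dose to be adjusted, so this is an illustration under that assumption.

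**Effect on the SAP bands**
- Text at week 6 without CR: 0.50 falls in 0.26-0.50 mg/kg/d.
- Table at week 6 without CR: 0.25 falls in ≤ 0.25 mg/kg/d.
- Change from baseline, following the text throughout: 1.0 to 0.50, top band to 0.26-0.50, decreased.
- Change from baseline, following the table throughout: 0.50 to 0.25, band 0.26-0.50 to ≤ 0.25, decreased.

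The change lines assume that the baseline dose is the starting dose. The percentage reduction is 50% on either version. SAP 11.4.2.3 takes the preceding treatment line when a new one starts on the visit date, so a dose begun at the W6 visit would first appear at W14.

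**The case against.** The strongest reply is that Table 1 prescribes nothing. It is a guideline, the investigator sets the regimen, qod is optional, and the no-CR row itself allows adjustment. That stands as far as the word goes: the table lists doses, and some variation between sites is permitted on purpose. It does not reconcile the passages. The text converts between alternate-day and daily dosing; the table does not. A site that chooses daily dosing and keeps the printed figure gives twice what a site using qod gives, and nothing says which amount the figure represents.

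It can also be said that the week-0 row is isolated, since every other statement of the starting dose is 1 mg/kg/day. That makes it less likely that sites halved the start, but the row still contradicts those statements.

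A reader might infer more than the documents support:

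- **That the end of the taper conflicts (week 16 against week 20).** Stopping after two weeks at the last level is permitted, not required, so the table's week-20 end can coexist with it.
- **That text and table differ by 59.5 against 29.75 mg/kg over the whole taper.** These are two readings of one table: 14 × (1.0 + 0.75 + 0.65 + 0.50 + 0.40 + 0.30 + 0.20) + 42 × 0.15 = 59.5, and half of that. The text gives no separate doses for weeks 2-6 or for the CR taper. With weeks 0-2 daily and the rest qod, the total is 14 + 45.5 ÷ 2 = 36.75 mg/kg.
- **That the conflict decides the steroid-sparing endpoint.** That endpoint is descriptive, and the change class and percentage reduction at week 6 agree on either version. The absolute bands differ, and they record the dose actually taken.

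**Conclusion.** The contradiction is real and should be fixed. Section 6.2 and its SAP copy state prednisone doses that differ two-fold at week 0 and at week 6 without CR, if qod in Table 1 is read literally. The discretion clauses permit either exposure without reconciling the two.

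The size is a possible range. The documents do not show which dose any site gave, so neither a difference between sites nor a shift in the M6 response can be claimed; the documents give no basis for the size or direction of such a shift. The A'Hern sample size and the primary test are not affected. What is affected is the reader's ability to know what background treatment the response rate reflects, and the meaning of the absolute dose bands.

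**What to change.** 1. **Reconcile the documents.** Align the 6.2 text, Table 1 (header and qod labels) and SAP 9.3.6.2. Use one unit convention in every row, either amount per dose with its frequency or mean mg/kg/day, and state the same week-0 dose and the same week-6 no-CR dose in text and table. The clinical team decides which figures stand.

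2. **Describe what was given.** For patients already treated, summarise actual mean prednisone in mg/kg/day from first ATO infusion to M6, beside the M6 response. The SAP comes close but does not plan this: 11.4.2.3 gives bands at visits, and 11.3.2 averages over the whole treatment duration. Neither is set against response.

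The cost is one clarifying amendment with matching SAP text, and one descriptive table from dose and frequency data already collected. No extra patients or procedures are needed. The planned last visit was June 2020 and the SAP response algorithm is dated 19 October 2020. If treatment is complete, the amendment can no longer change exposure and the descriptive table is the part that matters.

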### **6.3.Preventive treatments for infections**

- Antibiotic prophylaxis for prevention of Pneumocystis pneumonia and infections with encapsulated organisms must be given to all patients until 6 months after discontinuation of all systemic immunosuppressive treatment. Suggested antibiotic regimens are: Trimethoprim/Sulfamethoxazole DS 1 tab PO qMWF, or if sulfa allergic, Atovaquone 1500 mg PO qMWF or Pentamidine 300 mg inhaled q4 weeks. Additional prophylactic antibiotics are at the discretion of the physician.
- Prophylactic antiviral and antifungal medications must also be given until the steroid dose is stable < 0.15 mg/kg/day. All patients who are at risk of CMV infection should be monitored for occult CMV infection, and appropriate treatment should be instituted per institutional practice. Populations at risk of CMV infection include all CMV-seropositive patients, all CMV-seronegative patients with CMV-seropositive donors, and all patients receiving blood product transfusions from CMV-seropositive donors.
- Antifungal prophylaxis: No specific antifungal prophylaxis is recommended. In case it is the routine policy of a centre to give an antifungal prophylaxis in patients with chronic GvHD (i.e., fluconazole, oral amphotericin B, itraconazole, posaconazole or other drugs for which there are published data of controlled trials showing the antifungal prophylaxis of this drug in allo-SCT patients), it is required that this policy is being documented in the CRF and the same policy be applied to all the patients included in the centre.
- In all cases, physicians can refer to the recommendations made by the European Conference on Infections in Leukemia (ECIL). The full version is available on the website of the EBMT:

<https://www.ebmt.org/Contents/Resources/Library/ECIL/Pages/ECIL.aspx>

- All treatments given for prevention of infectious complications must be reported in the electronic CRF of the study.

#### **6.4. Prohibited concomitant treatments**

- Patient receiving mycophenolate mofetil
- Any other investigational study drugs than ATO

## 7. Study procedures: inclusion procedure, treatment schema and calendar of evaluations

Patients will undergo the procedures and examinations which must be performed as shown in the following flow chart:

**Table 2. Study Summary**

	Selection (V1) (10 days before ATO treatment)	During ATO treatment (1 st and 2 nd cycles)	Every 2 weeks (from M2 to M3) +/- 5 days	Every month (M4, M5, M6) +/- 5 days	At 6 and 14 weeks and every 3 months (M6, M9, M12) +/- 5 days	Study drop- out +/- 5 days
Information and patient consent	*					
Inclusion/exclusion criteria check	*					
Socio-demographics	*					
Concomitant diseases	*					
Recipient, Donor and Transplant characteristics 	*					
Diagnosis & Scoring of chronic GvHD	*					
Chronic GvHD activity assessment form A	*				*	*
Chronic GvHD activity assessment form B	*				*	*
Lee Symptom scale	*				*	*
FACT-BMT	*				*	*
Physical examination	*	* 	*	*	*	*
EKG – QTc  measurement	*	* 	*			
Hematology 	*	* 	*	*	*	*
Biochemistry 	*	* 2/9	*	*	*	*
Coagulation test 	*	* 	*	*	*	*
Infectious disease surveillance	*	* 		*	*	*
Serum immunoglobulin level	*			*	*	*

**Table 2. Study Summary (continued)**

	Selection (V1) (10 days before ATO treatment)	During ATO treatment (1 st and 2 nd cycles)	Every 2 weeks (from M2 to M3)	Every month (M4, M5, M6)	At 6 and 14 weeks and every 3 months (M6, M9, M12)	Study drop- out
Autoantibodies (AAN, ANCA)	*	* 		*	*	*
Serum pregnancy test	*					
Immunological evaluation (Saint Antoine)	*	*			*	*
Pharmacokinetic evaluation		* 				
Pulmonary function test (FEV1)	*				*	*
Chest x-ray	*					
Cutaneous biopsy ( if relevant )	*					
ATO treatment ( date, dose, reason of change )		*				
Response to treatment					*	
Associated treatment(s) 	* 	*	*	*	*	*
Adverse event(s)		*	*	*	*	*

 During ATO treatment, must be performed daily before each ATO administration.

 Must be performed weekly.

 CBC included leucocytes, neutrophils, lymphocytes, monocytes, and eosinophils counts, hemoglobin and platelets.

 Biochemistry included measurement of glycaemia, creatinine, uric acid, calcium^1, potassium^1, magnesium^1, total protein, albumin, total bilirubin, alkaline phosphatases, SGOT, SGPT, and LDH.

 Prothrombin time [PT], activated partial thromboplastin time [APTT].

 Pharmacokinetic evaluation: the samples must be performed before each administration at D2, D3, D4, D5, D8, D12, D17 and D24 of cycle 1 and cycle 2 (if applicable).

 History of GvHD prophylaxis : documentation of any associated treatments and topical therapy since graft for acute GvHD or progressive form of cGvHD treated by corticotherapy < 1 mg/kg/day, whenever possible given collected clinical history

 Documentation of any associated treatments and topical therapy for chronic GvHD (including glucocorticoid creams, topical tacrolimus, oral beclomethasone or budesonide, topical azathioprine and ophthalmic glucocorticoids...)

 Must be performed twice a week.

 Documentation on the diagnosis of hemopathy requiring transplant and DLI modality.

## **7.1 Patients selection**

Only patients meeting the National Institutes of Health (NIH) criteria for chronic GvHD requiring systemic therapy are eligible for inclusion in this study (Jagasia et al., 2015) (see Appendix 1 for full details).

Allogeneic stem cell recipients who develop a first episode of chronic GvHD will be screened for eligibility. If they fulfill inclusion and exclusion criteria and give their informed consent (see Appendix 14), they will be included in the study.

### **7.1.1 Diagnosis of chronic GvHD**

Minimum one diagnostic manifestation of chronic GvHD OR presence of at least 1 distinctive manifestation plus a pertinent biopsy, laboratory, or other tests (eg, pulmonary function tests [PFT], Schirmer's test), evaluation by a specialist (ophthalmologist, gynecologist), or radiographic imaging showing chronic GvHD in the same or another organ, unless stated otherwise (see Appendix 1 and Appendix 2).

Differential diagnosis of chronic GvHD must be excluded e.g. toxicity, infection.

Diagnostic and distinctive manifestations of chronic GvHD can be found in the skin and appendages, mouth, eyes, genitalia, esophagus, lungs, and connective tissues. Biopsy or other testing is often valuable to confirm the presence of chronic GvHD, but is not always feasible and is not mandatory if the patient has at least one of the diagnostic findings of chronic GvHD. Thus, organ biopsies are per physician discretion.

### **7.1.2 Definition of mild, moderate and severe chronic GvHD**

Eight organs or sites (skin, mouth, eyes, gastrointestinal tract, liver, lungs, joint and fascia, and genital tract) are considered for calculating global score. Elements included in the proposed global scoring include both the number of organs or sites involved and the severity score within each affected organ. Performance status scoring is not incorporated into the global scoring system. Organ scoring is performed according to the NIH Working Group consensus (Jagasia et al., 2015) (see Appendix 2).

For skin, the composite score is split into 2 scores to document the extent of skin involvement (BSA) and the specific skin features, separately (see Appendix 6). The higher of the 2 scores is to be used for computation of global severity.

Eyes, are better assessed by a specialist, however, it is not mandatory.

For lung, pulmonary function tests to assess the first forced expiratory volume (FEV1) are mandatory in this protocol. The composite score is split in 2 score, a symptom score and a FEV1 score based. In case of discrepancy between both score, the FEV1 score is used for the final lung scoring.

For genital tract, scoring is based on severity of the signs instead of symptoms, both in man and woman, according to the figure provided in Appendix 3. Genital tract scoring must be performed by a specialist or a trained practitioner in chronic GvHD grading. Female or male genital GvHD is not scored if a practitioner is unable to examine the patient.

For joint and fascia, the photographic-range and motion (P-ROM) score is an exploratory measure and is not included in the calculation of global severity.

Abnormality present but explained entirely by non-chronic GvHD documented cause must be specified and the organ will be excluded from calculation of the global severity.

Computation of the chronic GvHD global severity, as mild, moderate or severe is indicated in the table below:

**Table 3. NIH global severity of chronic GvHD**

Mild	1 or 2 Organs involved with no more than score 1 plus Lung score 0
Moderate	3 or More organs involved with no more than score 1 OR At least 1 organ (not lung) with a score of 2 OR Lung score 1
Severe	At least 1 organ with a score of 3 OR Lung score of 2 or 3

Key points:

- In skin: higher of the 2 scores to be used for calculating global severity.
- In lung: FEV1 is used instead of clinical score for calculating global severity.
- If the entire abnormality in an organ is noted to be unequivocally explained by a non-GvHD documented cause, that organ is not included for calculation of the global severity. If the abnormality in an organ is attributed to multifactorial causes (GvHD plus other causes) the scored organ will be used for calculation of the global severity regardless of the contributing causes (no downgrading of organ severity score).

